## 8. Flow-up

		1 day	1 week (±1 day)	2 weeks (±1 day)	4 weeks (±3 days)	8 weeks (±3 days)	12 weeks (±7 days)	>24 weeks
Subjective perception	Comfort	√						
	Bleeding	√						
	Epiphora, mucopurulent discharge	√	√	√	√	√	√	√
Specimen collection	conjunctival sac		√	√	√	√		
	nasal cavity				√			
Endoscope						√	√	√

## 9. Expected Risks and Measures to Address Them

1) En-DCR is an invasive procedure and there is a risk of blood leakage from the lacrimal sac-nasal anastomosis in the early postoperative period.

Most of the distant cases fail due to mucosal epithelial tissue hyperplasia, scarring and obstruction of the anastomosis. HBCS can stop diffuse bleeding, inhibit bacteria, and promote wound healing, etc. 5-FU can effectively inhibit the proliferation of fibroblasts. However, the effect of the two as dressings at the anastomosis of the lacrimal sac and nasal mucosa applied to En-DCR is uncertain. We will take appropriate measures if the following situations occur.

- a. Localized infection: intensive anti-infection treatment.
- b. Severe postoperative bleeding: Use other drugs and dressings to stop bleeding.
- c. Granulation tissue, scar proliferation and anastomotic adhesion: excise or separate them, and apply antiproliferative drugs to the wound.
- d. Delayed healing: use other dressings and medications.

2) Adequate and repeated education, obtaining informed consent, establishing timely and effective communication with patients, and standardized follow-up.

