## **The impact of hydroxybutyl chitosan and 5-Fluorouracil on the procedure of endoscopic endonasal dacryocystorhinostomy.**

### **1. Background**

Endoscopic endonasal dacryocystorhinostomy (Endo-DCR) has the advantages of less surgical trauma, shorter time, less postoperative bleeding, faster recovery, and no skin scarring. However, the success rate of Endo-DCR surgery still varies widely between 58% and 94%, and the reason for surgical failure is mainly due to the membranous closure of the lacrimal sac-nasal anastomosis. The application of new filling materials to the lacrimal sac-nasal anastomosis provides a new way to improve the success rate of Endo-DCR.

Chitosan (CS) is a natural cationic polysaccharide, chemically named poly-2-amino-2-deoxy B-D-glucose, which has good biocompatibility and biodegradability, and is a new type of natural medical biomaterials. CS also has the advantages of abundant sources, no need for refrigeration, can be sterilized by autoclaving, and low price. Several studies have demonstrated the safety and efficacy of CS products for Endo-DCR. CS as hemostatic dressing for Endo-DCR is superior to collagen hemostatic agents. The success rate of CS-assisted Endo-DCR is higher than that of unassisted control group. However, chitosan is not easily soluble in water, making its application somewhat limited.

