## 7. Study Endpoint

The end of 6 months after surgery was used as the study endpoint.

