## **10. Statistical methods**

To compare the differences between the adjuvant therapeutic effects of different En-DCR in the three groups: data were analyzed using SPSS 19.0 software, one-way ANOVA was used for age comparison, and Kruskal-Wallis H-test was used for comparison of postoperative comfort and blood leakage. Comparison of gender, complications, and cure rate

was performed by chi-square test, and the difference was considered statistically significant at  $P<0.05$ . Effective rate was compared by Fisher's exact probability method, and  $P<0.05$  was regarded as statistically significant difference, and  $P<0.0167$  was regarded as statistically significant difference for two-by-two comparison. The collected conjunctival sac and nasal flora were analyzed: alpha diversity analysis, PCA analysis, taxonomic composition analysis, and Lefse analysis were used, and differences were considered statistically significant at  $P<0.05$ . Comparisons between groups were made using chi-square test or fisher's exact probability method for adverse events and serious adverse events when necessary.

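### Do the undefined cure and effective rates, with no scoring rule for patients re-treated before 6 months, require a change to the plan?

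*Combined protocol and SAP*

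**What the plan says.** Section 7 sets the time of assessment: "The end of 6 months after surgery was used as the study endpoint". It attaches no outcome variable to that time. Section 8 schedules "Epiphora, mucopurulent discharge" at every visit and endoscopy at 8 weeks, 12 weeks and the last visit, which is listed as later than 24 weeks.

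Section 10 names two efficacy outcomes. One appears in the list "Comparison of gender, complications, and cure rate", tested by chi-square at 0.05. For the other, "Effective rate was compared by Fisher's exact probability method", with 0.05 for the overall test and a limit of 0.0167 that "was regarded as statistically significant difference for two-by-two comparison". Neither rate is defined, and nothing separates one from the other.

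Section 9 gives the measure for late tissue problems: "Granulation tissue, scar proliferation and anastomotic adhesion: excise or separate them, and apply antiproliferative drugs to the wound". It names no drug, arm or time. The same section says "Most of the distant cases fail due to mucosal epithelial tissue hyperplasia, scarring and obstruction of the anastomosis", and section 1 says "the reason for surgical failure is mainly due to the membranous closure of the lacrimal sac-nasal anastomosis".

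Section 4 lets patients leave because efficacy is unsatisfactory. It does not say whether they stay in the denominator.

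**The concern.** Re-treatment under section 9 acts on the process that the protocol itself names as the main cause of failure. Endoscopy at 8 and 12 weeks can reveal scarring or adhesion, and treating it then may leave the anastomosis open at 6 months. Nothing in section 10 prevents that patient from being counted as cured.

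Two questions are then mixed: did the dressing succeed without help, and what was the state at 6 months with all care included? The same patients can give different answers. An unwritten rule can be chosen after results are known. If rescue is equally common among failures in all arms, counting it as success pulls the arms together; if it is unequal, the shift can go either way. Control or group A patients might also receive a drug of the kind that distinguishes group B. That is only a possibility, since section 9 names no drug and refers to application to the wound, while group B's 5-FU is injected during surgery.

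**Working it through.** **The plan's own figures.** Section 5 gives 3 × 40 = 120. The pairwise limit is 0.05/3 = 0.0167. Both are consistent. The 40 per group cannot be re-derived, because no design rates, target difference or power are stated.

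**Inputs for the illustration.** n = 40 per arm and the test limits come from the documents. Everything else is assumed: success without re-treatment of 70% (control), 80% (A) and 90% (B), and a share r of failures that are re-treated and scored as successes. Section 1 gives only a general success range of 58% to 94%.

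**Formula.** The scored rate is p′ = p + r(1 − p). With equal r in two arms, the difference shrinks by the factor (1 − r). For r = 0.50: control 0.70 + 0.50 × 0.30 = 0.85, group B 0.90 + 0.50 × 0.10 = 0.95, so 20 points become 10.

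**Power by exact enumeration, two-sided, same r in every arm.**

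| r | Control v B, scored | Fisher, 0.0167 | Three-group chi-square, 0.05 |
|---|---|---|---|
| 0 | 70.0% v 90.0% | 34.5% | 50.8% |
| 0.10 | 73.0% v 91.0% | 28.9% | 44.9% |
| 0.25 | 77.5% v 92.5% | 21.2% | 36.1% |
| 0.50 | 85.0% v 95.0% | 9.6% | 22.5% |

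**Unequal rescue.** Half of control failures only: 85% v 90%, Fisher power 2.1%. Half of group B failures only: 70% v 95%, 66.8%. With 70% in all arms and half the failures rescued in one arm (85% v 70%), one chosen pair is significant by Fisher in 14.6%, against 0.85% with no rescue. The three-group chi-square gives 34.4% against 5.0%. Those two tests are not like for like. Nor are the significant results all false: under the all-care question the difference in 6-month status is real.

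**A borderline table.** 28/40 v 38/40 gives Fisher P = 0.0064. Scoring two re-treated control patients as successes gives 30/40 v 38/40, P = 0.025, above 0.0167. The effective rate also has an overall test at 0.05. With control at 30 and group B at 38, the three-group Fisher P stays below 0.05 for every group A count from 26 to 40 (largest 0.0485, at 34). The overall result stands and this pairwise claim changes.

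**The opposite error.** Suppose re-treatment is always scored as failure and 10% of open anastomoses are wrongly counted as failed. In both arms: 0.70 × 0.9 = 63% v 0.90 × 0.9 = 81%, and Fisher power goes from 34.5% to 19.9%. In control only, 63% v 90%, it becomes 61.1%. In group B only, 70% v 81%, it becomes 6.5%. With 70% in all arms, over-counting in control alone raises the chance of a significant result from 0.85% to 2.4% (Fisher, that pair) or from 5.0% to 9.6% (three-group).

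**Reading the sections together.** Section 7 fixes 6 months, so the open-ended last visit in section 8 leaves a loose window, not an unlimited period. The symptom and endoscopy items are both collected at that visit. Section 10 compares complications and adverse events between arms, so differences in scarring or re-treatment may be seen there, although that does not settle how they are scored.

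**The case for a change.** The strongest case for a change is that the two efficacy outcomes are names without content, that re-treatment acts directly on what they presumably measure, and that no other section closes the gap. The exit rule for a changed surgical procedure does not mention postoperative re-treatment and would lead to exit, not to a score. Writing the rule down before analysis costs little, and two patients can move a pairwise result across 0.0167.

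Much of this stands. The definitions are absent, the scoring rule is absent, patients who withdraw for poor efficacy have no stated place in the denominator, and a late choice of rule is possible. It does not follow that the plan as written is wrong. Either reading answers a sensible question. Making re-treatment count as failure puts a decision with no described masking or threshold into the main outcome, and the opposite-error figures show that this can distort as much as the gap itself. Asking for the two rates to be defined, without criteria and without saying how cure differs from effective, names the gap but does not fill it. The drug-overlap point remains a possibility that the documents neither confirm nor exclude.

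**Conclusion.** No change follows. This is an unwritten definition and an unwritten scoring rule, not a stated rule that produces a wrong result. An analyst would fill it from the symptom and endoscopy items at the 6-month visit, and a reader of the report would expect the definition used, the denominator and the number re-treated per arm to be stated. Which scoring comes first is a trade-off between two legitimate questions.

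The documents do not allow the size to be estimated. Under assumed success of 70/80/90% and equal rescue, pairwise Fisher power (control v B) runs from 34.5% with no rescue to 9.6% with half of failures rescued; if few patients are re-treated, the effect is small. The illustration uses the same assumed rates for cure and for effective, although the plan treats them as separate outcomes. It says nothing about the effect of the missing definitions themselves. The conclusion would weaken if re-treatment proved frequent and clearly unequal between arms.

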## **10. Statistical methods**

To compare the differences between the adjuvant therapeutic effects of different En-DCR in the three groups: data were analyzed using SPSS 19.0 software, one-way ANOVA was used for age comparison, and Kruskal-Wallis H-test was used for comparison of postoperative comfort and blood leakage. Comparison of gender, complications, and cure rate

was performed by chi-square test, and the difference was considered statistically significant at  $P<0.05$ . Effective rate was compared by Fisher's exact probability method, and  $P<0.05$  was regarded as statistically significant difference, and  $P<0.0167$  was regarded as statistically significant difference for two-by-two comparison. The collected conjunctival sac and nasal flora were analyzed: alpha diversity analysis, PCA analysis, taxonomic composition analysis, and Lefse analysis were used, and differences were considered statistically significant at  $P<0.05$ . Comparisons between groups were made using chi-square test or fisher's exact probability method for adverse events and serious adverse events when necessary.

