#### **5. Test Groups**

The trial was divided into 3 groups, 40 cases were to be collected in each group, totaling 120 cases.

1) Control group: gelatin sponge wrapped thrombin and tobramycin dexamethasone ophthalmic ointment group.

2) Test group A: temperature-sensitive hydroxybutyl chitosan (HBCS) group

3) Test group B: HBHS combined with 5-fluorouracil (5-FU) group

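### Pairwise effective rates: Boschloo's exact test at the plan's P<0.0167 would keep every Fisher rejection and add up to about 8 power points (about 6 within the 58% to 94% background range)

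*Combined protocol and SAP*

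**What the plan says.** Section 10 (Statistical methods) gives the test for this outcome: "Effective rate was compared by Fisher"'s exact method. It then gives two thresholds. P<0.05 applies, by context, to the three-group comparison. P<0.0167 "was regarded as statistically significant difference for two-by-two comparison". No separate test is named for the pairs, so Fisher's test is read as applying to them too.

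Section 5 (Test Groups) fixes the arm sizes: "40 cases were to be collected in each group, totaling 120 cases".

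The plan does not define effective rate. It does not state sidedness, expected rates or power, or say whether pairs are tested only after a significant three-group result. The only figures for success are in section 1 (Background): "the success rate of Endo-DCR surgery still varies widely between 58% and 94" per cent.

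**The concern.** The design fixes the number of patients in each arm. It does not fix the total number of successes. Fisher's test conditions on both, so with 40 per arm only a limited set of P values can occur, and the true error falls well below the nominal level.

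Boschloo's test takes the Fisher P value as its statistic but computes the error with only the arm sizes fixed. It therefore suits the sampling scheme and can use more of the 0.0167.

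The pairwise contrasts are how the plan would separate chitosan alone, chitosan with 5-FU, and control. With 40 per arm and no stated power, part of the power for those contrasts is given up without any gain in type I error protection that the plan asks for.

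**Working it through.** **Inputs.** 40 v 40 (section 5). Fisher's exact test and pairwise threshold 0.0167 (section 10). Two-sided testing is assumed. Success rates are assumptions, shown over a range, with 58% to 94% (section 1) as the reference.

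**1. The plan's threshold.** 0.05 / 3 = 0.01667, which rounds to 0.0167. The stated figure is reproduced as a Bonferroni split over three pairs.

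**2. Fisher's true error.** For x and y successes in two arms of 40, with t = x + y, the Fisher P value sums C(40,i)·C(40,t−i)/C(80,t) over all i whose term is no larger than the observed one. The true error at a common rate p is the sum, over tables with Fisher P < 0.0167, of Bin(x; 40, p)·Bin(y; 40, p). Enumerating all 41 × 41 = 1,681 tables:
- Fisher rejects 946 tables.
- The maximum true error is 0.97%, at p = 50%.
- For p between 58% and 94% the true error runs from 0.17% to 0.90%.

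**3. Boschloo's true error.** The Boschloo P value is the maximum over p of Pr(Fisher P ≤ observed Fisher P). Given any total t, that probability is at most the observed Fisher P. The average over t is then also at most that value, so the Boschloo P never exceeds the Fisher P and no Fisher rejection can be lost. The enumeration agrees:
- Boschloo rejects 982 tables: 0 lost and 982 − 946 = 36 gained.
- The maximum true error is 1.58%, below 1.67%.
- Example: 25/40 v 35/40 has Fisher P 0.0188 (not significant at 0.0167) and Boschloo P 0.0104 (significant).

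**4. Power at two-sided 0.0167, 40 v 40.** Power is the sum of Bin(x; 40, p1)·Bin(y; 40, p2) over rejected tables.

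| Rates | Fisher | Boschloo | Gain (points) |
|---|---|---|---|
| 47% v 74% (largest overall) | 44.6% | 52.9% | 8.3 |
| 58% v 83% (largest within 58% to 94%) | 43.8% | 50.1% | 6.3 |
| 65% v 88% | 42.6% | 48.3% | 5.7 |
| 70% v 90% | 34.5% | 39.1% | 4.6 |
| 75% v 94% | 39.2% | 41.6% | 2.5 (before rounding) |
| 58% v 94% | 92.2% | 94.0% | 1.8 |
| 80% v 95% | 25.6% | 26.5% | 0.8 (before rounding) |
| 85% v 97% | 17.3% | 17.4% | 0.1 |

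The mean gain over pairs of rates within 58% to 94% is 2.4 points. With both rates between 75% and 99%, the mean is 0.6 and the maximum 2.9.

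**5. In patients.** For Fisher to match Boschloo's power, it needs about 45 per arm at 58% v 83%, and 43 to 44 at 70% v 90%. The change is worth roughly 3 to 5 patients per arm in those cases.

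**6. Unequal arms.** With 38 v 36 analysed at 0.0167, no Fisher rejection is lost and 20 tables are gained.

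**7. All three pairs together.** If all three are tested without first requiring a significant three-group result, the maximum family-wise error is 2.6% with Fisher and 4.2% with Boschloo. The simple bound 3 × 1.58% = 4.74% is also below 5%.

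**The case against.** Fisher's test is valid, widely recognised and compatible with the software the plan names. The choice between conditional and unconditional exact tests is a legitimate methodological one, and section 10 contains no contradiction or miscalculation here. The gain is often small: at 0.0167 it nearly disappears when both rates are high, and high rates may well be what this surgery achieves. The change also brings in a second package, and it pairs a conditional three-group test with unconditional pairwise tests. An undefined effective rate and the absence of a power statement matter more.

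Most of this stands, and it limits the point to a minor improvement. It does not remove the gain: at the same nominal level, Boschloo rejects whenever Fisher does and in 36 further tables.

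A reader might infer a larger benefit by working at 0.05. There, Fisher's maximum true error is 3.3%, Boschloo's is 4.8%, and power at 85% v 97% rises from 29.0% to 39.8%. The documents do not support using those figures for the pairs, because section 10 judges pairs at 0.0167. At that level the same scenario gains about 0.1 point. A reader might also infer that Boschloo helps most when success rates are very high. At 0.0167 the reverse holds: the larger gains come at lower rates.

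**Conclusion.** The point holds as an efficiency suggestion. At 40 v 40 and two-sided 0.0167, Fisher's true error is at most 0.97%. Boschloo's is at most 1.58%, with every Fisher rejection kept. The power gain is at most about 8 points over all pairs of rates, at most about 6 within the Background's range with a mean of about 2, and about 1 or less for contrasts such as 80% v 95%.

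These figures assume two-sided tests, all 40 patients per arm analysed, and pairwise tests that do not depend on the three-group result. The rates are illustrative, since the plan gives no design rates. The analysis in section 10 is not wrong as it stands, and a reader should not conclude that Fisher's test is invalid or that the trial's type I error is at risk.

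**What to change.** In section 10, before any outcome is seen, state that the two-by-two comparisons of effective rate use the two-sided Boschloo exact test at P<0.0167, with the two-sided Fisher P value as its statistic. Keep Fisher's exact test (Freeman-Halton) for the three-group comparison at P<0.05. The definition of the two-sided P value should be written out, because the guarantee of losing no Fisher rejection rests on it and software may define it differently when arms are unequal.

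The cost is one sentence, a free routine outside SPSS 19.0 (for example in scipy or R), and a test name that fewer readers will know. No extra patients or data are needed.

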## **2. Aims:**

To investigate the effects of HBCS with and without 5-FU during Endo-DCR.

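### Effective rate: a gated three-group Fisher procedure gains power over the flat P<0.0167 rule under the same 5% ceiling. Cure rate: pairwise tests are needed to isolate 5-FU.

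*Combined protocol and SAP*

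**What the plan says.** All the testing rules are in Section 10 (Statistical methods).

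- **Effective rate.** "Effective rate was compared by Fisher's exact probability method", at P<0.05 overall, while P<0.0167 "was regarded as statistically significant difference for two-by-two comparison". The section does not say whether the pairwise tests require a significant overall test, and it names no stepwise or closed procedure.
- **Cure rate.** It shares a sentence with a baseline variable and a safety outcome: "Comparison of gender, complications, and cure rate" "was performed by chi-square test, and the difference was considered statistically significant" at P<0.05. That sentence has no pairwise test or pairwise threshold.

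Section 5 (Test Groups) fixes the size: "40 cases were to be collected in each group, totaling 120 cases". The arms are control, A (HBCS) and B (HBCS plus 5-FU). Section 2 states the aim: "To investigate the effects of HBCS with and without 5-FU during Endo-DCR". The contrast of B with A lies inside that aim.

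**The concern.** There are two separate points.

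For effective rate, dividing 0.05 by three controls error but is stricter than a three-group design requires. In a trial of 40 per arm this costs power on every pairwise question. It also more often produces an awkward result: a significant overall test with no pair that can be named as different.

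For cure rate, a three-group test says only that the arms are not all alike. It cannot separate a benefit of HBCS from a benefit of adding 5-FU. Section 9 (Expected Risks) itself says that "the effect of the two as dressings at the anastomosis of the lacrimal sac and nasal mucosa applied to En-DCR is uncertain". If no pairwise test is prespecified, any claim about 5-FU on cure rate would be chosen after the data are seen.

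**Working it through.** **The plan's figure.** Three pairs share 0.05: 0.05/3 = 0.01667, which rounds to the stated 0.0167.

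**Inputs.** 40 per arm (Section 5); overall 0.05 and pairwise 0.0167 (Section 10). Tests are taken as two-sided, because sidedness is not stated. The plan gives no design rates, so power uses assumed rates (control/A/B) across the 58% to 94% success range in Section 1. The grid has control ≤ A ≤ B in 6-point steps, with the compared arms at least 6 points apart.

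**Why the gated rule is valid.** Call the pairwise nulls A = control, B = control and B = A. Any two of them together imply that all three arms are equal. The only intersection hypothesis is therefore the three-group null. Testing it at 0.05, and then each pair at 0.05 only if it is rejected, is a closed test with family-wise error at most 5%.

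**Method.** All 41³ = 68,921 outcome tables (x, y, z) were enumerated. For a total of m successes, the exact three-group Fisher (Fisher-Freeman-Halton) P value sums C(40,x)C(40,y)C(40,z)/C(120,m) over tables no more probable than the one observed. Pairs use the 2x2 version. Power or error is the sum of the products of the three binomial probabilities over the rejected tables. Chi-square is Pearson's without correction.

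**Maximum family-wise error, 40/40/40**

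| Rule | All arms equal | Two equal, one different |
|---|---|---|
| Flat 0.0167, Fisher | 2.6% | 1.0% |
| Gate 0.05, then pairs 0.05, Fisher | 4.6% | 3.3% |
| Pairs at 0.05, no gate, Fisher | 8.4% | not needed |
| Gate 0.05, then pairs 0.05, chi-square | 5.5% | 5.9% |

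**Rejections, 40/40/40.** The flat rule rejects 38,786 tables for each pair. The gated rule keeps all of them and adds 4,236, giving 43,022. With the uneven arms checked, at most 4 tables are lost for any pair (for example 4 of 29,438 at 34/40/36), and gated error is at most 4.95%.

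**Pairwise power, flat to gated, 40/40/40**

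| Control/A/B | A v control | B v control | B v A |
|---|---|---|---|
| 58/75/94% | 15.1% to 27.9% | 92.2% to 95.7% | 39.2% to 57.6% |
| 70/85/95% | 14.6% to 27.8% | 66.8% to 77.1% | 9.6% to 18.0% |
| 85/95/98% | 9.6% to 18.2% | 22.9% to 35.9% | 0.2% to 0.6% |

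Over the grid the gains are:

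- B v A: 2 to 18 points, median 8 (56 scenarios)
- B v control: 2 to 16 points, median 9 (77 scenarios)
- A v control: 2 to 18 points, median 7 (56 scenarios)

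**Overall Fisher significant but no pair named.** At 70/85/95% this happens in 10.1% of trials under the flat rule and 0.1% under the gated rule. Over 77 scenarios the ranges are 1.2% to 15.0% (median 8.6%) and 0.0% to 2.4% (median 0.1%).

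**Cure rate, chance of a significant three-group chi-square**

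- 58/94/94% (5-FU adds nothing): 99.3%
- 58/58/94% (HBCS alone adds nothing): 99.2%
- 70/90/90% (5-FU adds nothing): 67.2%. In 65.6% of trials the overall test is significant while B v A has Fisher P ≥ 0.05.

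The first two scenarios give opposite answers about 5-FU but the same overall result.

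**The case against.** The strongest reply is that the effective-rate rule contains no error. It is a valid Bonferroni correction, and replacing it is a refinement. That is right, and the point is put as an improvement.

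The benefit is also bounded. On the 56-scenario grid, median gated power for B v A is only about 18%. It is below 50% in 77% of scenarios and reaches 80% in 7%. The example of 39% to 58% sits at the top of the range of gains. Neither rule rescues contrasts that 40 per arm cannot detect. The documents define neither effective rate nor cure rate, so the background range may not apply; near the ceiling the B v A gain almost vanishes. These limits stand for power. The closed-test argument and the absence of lost rejections at 40 per arm do not depend on the assumed rates.

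The flat rule's unused error is smaller with uneven arms: its maximum is 3.2% at 38/36/40 and 34/40/36, against 4.9% gated. Ungated error there is 9.2% to 9.8%, which strengthens the case for a written gate.

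The 0.0167 clause could be read as covering cure rate too. Its place in the effective-rate sentence argues against that, and a clarifying sentence would be needed either way. Section 9's uncertainty concerns both materials as dressings, so the aim in Section 2 is the better support for the B v A contrast.

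Finally, keeping 0.0167 as the cure-rate default leaves the problem of no named pair (17.9% at 70/90/90%, against 0.4% with the gated alternative). That is a real trade-off: the default leaves the planned chi-square untouched, and the alternative replaces it.

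**Conclusion.** Both parts hold. For effective rate, the flat rule at 40 per arm uses about half of the 5% error allowed (2.6%, against 4.6% gated). It gives up a median of 7 to 9 points of pairwise power on the assumed grid, and very little for B v A near the ceiling. For cure rate, the plan as written has no test that can attribute a difference to 5-FU.

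The present rule is not invalid, but both changes should be made. The power figures rest on assumed rates, two-sided tests and complete data. With 36 per arm, the B v A gain at 58/75/94% is similar (33.0% to 50.4%). Error is controlled within each outcome, not across the two.

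**What to change.** Make these changes before any outcome comparison is seen; loosening a threshold afterwards would not be defensible.

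- **Effective rate.** State that the three-group Fisher test at P<0.05 is a gate. Only if it is significant are A v control, B v control and B v A each tested by Fisher at P<0.05. The gate must be explicit.
- **Cure rate, default.** Keep the overall chi-square and add the same three comparisons by Fisher at P<0.0167. At 40 per arm every pair passing 0.0167 also has overall chi-square P<0.05, so the two rules cannot conflict.
- **Cure rate, alternative.** Use the all-Fisher gated rule and disclose that it replaces the chi-square. Do not gate at 0.05 with chi-square tests.
- **Reporting.** Give the three risk differences with Newcombe 95% confidence intervals, labelled unadjusted and descriptive, and state that the tests govern significance. In 20% to 29% of trials in the scenarios checked, at least one interval excludes zero where the gated rule is not significant. State also that error is controlled within each outcome only.

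The cost is a few sentences, with no added patients, visits or data. For effective rate, actual maximum error rises from 2.6% to 4.6%, within the same ceiling. The cure-rate default leaves the overall test unchanged. The alternative changes the chance of a significant overall result by -4.6 to +1.2 points on the 58-94% grid (67.2% to 63.2% at 70/90/90%), with a larger fall above it (33.9% to 23.4% at 92.5/99/99%).

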Hydroxybutyl chitosan (HBCS), a CS ether synthesized by substituting hydroxybutyl for the hydroxyl and amino groups of CS, maintains the nontoxic, biocompatible, biodegradable, antimicrobial, and moisturizing properties of CS, and the hydroxybutylation confers water-solubility and temperature-sensitivity to CS. Therefore, it is also widely used in biomedical applications such as postoperative adhesion prevention, tissue engineering, drug delivery and wound healing, etc. Materials made of HBCS, complexes of HBCS, and derivatives of HBCS have been shown to be safe and effective wound dressings with antimicrobial and blood coagulation promoting effects. Used for this trial proposed to be used is a heterophasic system of synthesized hydroxybutyl chitosan, this HBCS undergoes a sol-gel transition at a critical temperature (37 degrees Celsius), which facilitates clinical manipulation while accurately localizing around the anastomosis, preventing postoperative adhesions, and inhibiting the growth of fibroblasts. The role of HBCS in wound healing has been shown to have definitive therapeutic efficacy in clinical applications, and in ophthalmology also has some applications.

5-Fluorouracil (5-FU) is an antimetabolic drug that inhibits protein synthesis by suppressing the biochemical activities of rRNA and mRNA in the nucleus; it also induces the growth of apoptotic genes. In recent years, 5-FU has been found to be effective in the treatment of keloid

scars. It has now been widely used both at home and abroad to inhibit fibroblast proliferation and scar formation in the filtration vesicles after glaucoma filtration surgery, with good safety and efficacy. In antimetabolites as DCR adjuvant therapy significantly increased the size of the opening and improved the success rate of surgery.

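### Taxon-level flora tests, including LEfSe, are judged at P<0.05 with no correction for the number of taxa, and the flora results are not labelled exploratory

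*Combined protocol and SAP*

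**What the plan says.** Section 10 introduces the flora work with "The collected conjunctival sac and nasal flora were analyzed" and then sets one criterion for every method listed: "alpha diversity analysis, PCA analysis, taxonomic composition analysis, and Lefse analysis were used, and differences were considered statistically significant at" P<0.05. No false-discovery, Bonferroni or other adjustment is given for taxa, sites or visits. No flora measure or time point is named as the main one, and no LDA cut-off is stated for LEfSe.

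The only stricter level in section 10 is P<0.0167, which "was regarded as statistically significant difference for two-by-two comparison". It stands in the sentence on the effective rate.

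In the section 8 schedule, the "Specimen collection" rows tick the conjunctival sac at weeks 1, 2, 4 and 8 and the nasal cavity at week 4.

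The aim in section 2 is "To investigate the effects of HBCS with and without 5-FU during Endo-DCR", with no mention of flora. Section 7 places the endpoint well after the last flora sample: "The end of 6 months after surgery was used as the study endpoint".

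**The concern.** Taxonomic composition analysis and LEfSe compare the groups on many taxa at once. When each taxon is judged alone at 0.05, one null taxon in twenty is expected to pass by chance, and the list of passing taxa mixes real and chance differences with nothing to tell them apart.

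This matters because named-taxon differences are a likely reported result. The control dressing is the "gelatin sponge wrapped thrombin and tobramycin dexamethasone ophthalmic ointment group", and section 1 says HBCS "maintains the nontoxic, biocompatible, biodegradable, antimicrobial, and moisturizing properties of CS". A real flora difference is therefore plausible, but it gives no protection to the taxa that do not differ. The plan uses the language of statistical significance for flora just as it does for cure rate and does not call the flora results exploratory, so a reader could take each listed taxon as an established treatment effect.

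**Working it through.** **Inputs from the documents.** Flora threshold 0.05 (section 10); pairwise threshold 0.0167 (section 10); three groups of 40 (section 5); 4 conjunctival + 1 nasal = 5 site-visit sets (section 8).

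**Inputs assumed, because the documents do not give them.** Number of taxa (20 to 200), share of taxa truly different, size of the shift, within-patient correlation, and independence between taxa.

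**1. The plan's one adjusted threshold.** Three groups give three pairs, and 0.05/3 = 0.01667, which reproduces 0.0167. It corrects for pairs of groups only. Even if it were extended to flora, a null taxon tested on all three pairs would still have a chance of up to 3 × 0.0167 = 0.05 of passing. The number of taxa would remain uncorrected.

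**2. Expected chance passes in one set.** Expected count = number of null taxa × 0.05. Correlation between taxa does not change this count.

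| Assumed null taxa | Expected to pass P<0.05, one set | If all five sets are tested separately |
|---|---|---|
| 20 | 1 | 5 |
| 50 | 2.5 | 12.5 |
| 100 | 5 | 25 |
| 200 | 10 | 50 |

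All counts are before any LDA filter. The last column applies only if each set is tested on its own, which the plan does not state.

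**3. What a false-discovery adjustment does.** Simulation: Kruskal-Wallis test per taxon and set, 40 per group, five sets, independent taxa, within-patient correlation 0.5, a shift in one group. The figures are approximate, for about 100 taxa.

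| | Raw P<0.05 | BH within set | BH pooled over sets |
|---|---|---|---|
| True taxa declared, 0.8 SD (10% / 20% truly different) | 95% / 95% | 76% / 84% | 76% / 84% |
| True taxa declared, 0.5 SD (10% / 20% truly different) | 60% / 60% | 14% / 19% | 10% / 16% |
| False share of declared taxa, over these scenarios | 16% to 42% | 4% to 8% | 3% to 4% |

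BH is Benjamini-Hochberg at q<0.05. At raw P<0.05 the false share is lowest (about 16%) with 20% of taxa different by 0.8 SD, and highest (about 42%) with 10% different by 0.5 SD.

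**4. Within-set or pooled.** With every taxon null and five sets tested, at least one taxon is declared in about 16% to 19% of trials with within-set adjustment, against about 2% to 4% with pooling. That is a familywise measure across five sets. On the false share of declared taxa, the two options are close.

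**The case against.** The strongest reply is that little depends on these results. Flora is not in the aim, sampling stops at week 8 while the endpoint is at 6 months, and no success claim is tied to a taxon. The methods listed are largely descriptive or screening tools. All of this stands, and it limits the weight of the point.

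A second reply is that the plan does not say whether P is raw or adjusted, and that LEfSe normally adds an LDA step. An unqualified P<0.05 with no adjustment named is most naturally read as raw, and an analyst following the text would be free to use it so. An effect-size cut-off, which the plan does not state in any case, is not an error-rate control. It does mean that the counts above describe the P screen and not the final LEfSe list.

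A third reply is that correction is costly. This also stands. At a 0.5 SD shift most truly different taxa would no longer be declared, which is a heavy loss for a screening analysis. But raw testing is also at its worst there, with a false share of about 25% to 42%, so a smaller effect does not argue for leaving P unadjusted.

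Two stronger readings are tempting. A reader might infer that the trial will produce 25 or 50 false taxa. The documents do not support that, because they give neither the number of taxa nor separate testing of the five sets. A reader might also infer that one correction across both sites and all visits, with strict familywise control of alpha diversity, is required. For a secondary analysis outside the aim that is a choice, since within-set adjustment already brings the false share down to about 4% to 8%.

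**Conclusion.** The point holds as a minor, inexpensive improvement. As written, section 10 lets about 5% of truly null taxa through the P screen in each set tested, and 0.0167 cannot correct for the number of taxa. The 5% rate follows from the threshold itself; the counts of 1 to 10 per set rest on the assumed 20 to 200 null taxa. The false shares and sensitivity losses rest on the simulation model and should be read as illustrations. Nothing here bears on the cure-rate or effective-rate comparisons or on the 6-month endpoint. Confidence is medium, because the number of taxa, the handling of visits and the LEfSe settings are not stated.

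**What to change.** In section 10, for the taxon-level tests and the LEfSe P screen, replace P<0.05 with Benjamini-Hochberg q<0.05 across taxa, at least within each site-visit set tested and before any LDA step. State which visits are compared and whether separately. Label all flora results exploratory. Unadjusted P values may be shown alongside as descriptive.

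Optional: pooling the adjustment over all sets, which is stricter; Holm where alpha diversity is tested more than once; pairwise flora tests at 0.0167 only after a positive overall test; and a PERMANOVA beside the PCA.

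The cost is two or three sentences, with no added samples, visits or patients, and a little more analysis work because the adjustment may have to be run outside the LEfSe program. The real price is sensitivity: fewer truly different taxa will be declared, modestly so for large shifts and severely for moderate ones. The exploratory label and the descriptive P values keep those signals visible without calling them significant.
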